## **Outcome Measures**

We will collect the following data during this study.

At eligibility, medical records will be used to provide demographics and baseline information regarding the participant's cerebral palsy, its effects, comorbidities, impairments, and medications taken that might affect the results of this study.

Additionally, we will administer an End of Treatment Questionnaire (15 min) and collect usage and performance logs from the computer and stimulator device in an effort to determine the feasibility of cerebral palsy children using the treatment at home.

At enrollment, we will categorize the participant's general ability to handle objects in daily life using the Manual Ability Classification System (5 min). Using a flowchart, we ask the caregiver to identify which of five levels best describe the child's ability to handle age-appropriate objects. For example, level 1 is "Handles objects easily and successfully", level 2 is "Handles most objects but with somewhat reduced quality and/or speed of achievement", level 3 is "Handles objects with difficulty, needs help to prepare and/or modify activities", level 4 is "Handles a limited selection of easily manage objects in adapted situations, requires continuous support", and level 5 is "Does not handle objects and has severely limited ability to perform even simple actions. Requires total assistance."

At the end of each video game practice session (in lab and at home), we will assess game difficulty and engagement via self-report. A screen will appear at the end of each video game session (180 sessions) that asks the child to rate the difficulty and how engaged they were in the preceding session. The screen will show two visual analog scales (one for difficulty and another for engagement) for the child to report using the computer's touch screen.[6], [7] For difficulty, the choices are: very easy (face with a wide smile), easy (face with a narrow smile), neither easy or hard (neutral face), hard (face with a narrow frown), and very hard (face with a wide frown). For engagement, the choices are: very fun (face with a wide smile), fun (face with a

narrow smile), neither fun or fun or boring (neutral face), boring (face with a narrow frown), and very boring (face with a wide frown). The de-identified data will be saved to the USB drive along with game usage and performance data. This takes 30 seconds during a treatment session.

Additionally, we will assess the following hand muscle co-activation measures during lab visits prior to treatment:

Intervention outcomes that are assessed at baselines, end of treatment, and follow up will include the following.

- Melbourne Assessment 2: This is an assessment of unilateral upper extremity function for children ages 2.5 to 15. Participants will perform 14 tasks using their weaker arm and hand, each of which is scored on a 3,4 or 5 point scale. The tasks involve using the hand to reach different positions (reaching, pronation, supination) and manipulate pellets and crayons. This assessment takes 15 minutes to perform.[9]
- Finger movement tracking accuracy: Finger movement tracking is a method of measuring motor control. Using the same bend sensor used for controlling the video games, the relative degree of finger extension will be displayed as a cursor on a computer screen, its vertical position corresponding to the degree of finger extension. A sinusoidal trace having a frequency of 0.1 Hz (1 cycle in 10 seconds) will scroll across the screen. The amplitude of the sine-wave track will be scaled so that it oscillates between 15% and 85% of the participant's full active finger extension. The participant will be seated with the wrist and forearm stabilized in a neutral posture. The participant's task is to keep the cursor on or as close to the scrolling trace as possible by extending and flexing their index finger. The vertical distance between the cursor and the target trace will be calculated for every time point of data collected. The final error for each 30-sec trial will be the average vertical distance (percentage of the participant's range of motion) from the cursor to the target trace. Three trials will be administered after a practice trial, resting 1 minute between trials. This test takes approximately 5 minutes.
- Box and Block Test: The Box and Block test is a measure of gross manual dexterity, which requires the participant to pick up 1 block at a time, move it over a partition, and release it in a target area as many times as possible in a 1-minute period. The Box and Block test measures changes in functional grasp and release but not during activities of daily living (ADL), and therefore cannot be strictly categorized as either an impairment or activity limitation measure. This test takes approximately 5 minutes.
- Assisting Hand Assessment examines the ability of a child to use both hands during play tasks (such as wearing a hat, bang cymbals together, hold a bottle with one arm and manipulate marbles with the other, etc.) This test has two components, a score and a description of hand function. The score reflects how well the impaired hand assists the other and ranges from 22 points (if the impaired hand is not used at all) to 88 points (if the affected hand is used like a normal non-dominant hand). The descriptions detail whether the child grasps an object from the table or from the other hand, how stable objects are in the hand, and how quickly use of the affected hand is initiated relative to the other hand. This test takes 15-20 minutes to administer.
- Number of Hand Opening Repetitions will be counted during task practice and during video game play. During video game play, repetitions are detected by a change in the sign of the first difference (analogous to finger velocity) of the bend sensor signal. We will use the total number of repetitions for correlations.

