### Methods and Procedures

Both the experiment group and control group interventions last 6 weeks and consists of therapist-guided sessions in the rehabilitation clinic and self-administered or caregiver-assisted sessions at home. While both groups will receive the same task practice and video game training, only the experiment group will receive an electrical stimulation device to assist with hand opening during practice. An adaptive randomization algorithm will be used to balance the two groups with respect to age, gender, and baseline severity (not severe if the child is Manual Activity Classification System level I-II, severe if level III-V). The treatment dose will be the same for both groups: 10 sessions per wk of self-administered video game training at home plus 2 lab sessions per wk for the first 3 wks and 1 lab session per wk for the final 3 wks – 58 hrs total. Blinded assessment of upper limb impairment and function will be done at baseline, mid-treatment, end-of-treatment, and 3-mos post-treatment.

- Note: Contralaterally controlled electrical stimulation (CCFES) – Enables patients with upper extremity hemiplegia to open their paretic hand by stimulating finger and thumb extensors with surface electrodes. Stimulation is proportional to degree of unimpaired hand opening as detected by an instrumented glove worn on the unaffected hand. Thus, volitional opening of the non-paretic hand produces stimulated opening of the paretic hand. CCFES is used during functional task practice and hand therapy video games to link motor intent with execution.
- Note: Hand Therapy Video Games – Four intuitive and engaging games were developed specifically for play with CCFES to provide goal-oriented motor skill training, impairment-appropriate difficulty, and performance feedback that motivates iterative play and skill improvement. Paddle Ball (i.e., Pong) is a simplified tennis simulation that uses hand movement to control a vertically moving paddle. Skee Ball uses hand-opening speed to launch balls at targets. Sound Tracker requires the

hand to precisely follow a moving track generated by different songs. Marble Maze uses hand opening to rotate mazes and guide marbles out into a bucket.

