- i. Rehabilitation clinic sessions – These will occur up to twice per week for the first 3 weeks and once per week for the second 3 weeks of the 6 week treatment. They are therapist-guided and last up to 90 min consisting of 45 minutes of CCFES-mediated video games and up to 45 minutes of CCFES-mediated functional task practice. Early sessions will focus on training the patient and caregiver to self-administer play of a CCFES-mediated video game at home. As proficiency with one game develops, more games will be introduced. The functional task practice part of the session will engage the participant in using the CCFES system to assist them in practicing using their hand in activities such as lacing beads, throwing balls, eating finger foods, and other play and activities of daily living.
- ii. Home sessions – These consist of CCFES-mediated hand opening and video game exercises with caregiver assistance and supervision as needed. As proficiency develops and more games are added, each home session will increase in duration up to 90 minutes per day, as determined by the treating therapist based on the adherence of each participant. Self report of game difficulty and engagement will be made at the completion of each game (see below)

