### **Data analysis**

We will use a descriptive approach using means and standard errors to assess the effect of hand opening repetitions on the treatment group over time for each outcome. Due to the small sample size in our dataset, we will use a robust estimator to calculate the standard errors.

Upper extremity motor function will be assessed at enrollment, 6 weeks (end of treatment), and at 12 weeks post-treatment by a blinded assessor therapist. All assessments will be performed without any assistance from the stimulator and assessments will take place at least 24 hours after their last treatment session in order to avoid any transient carry-over effect or muscle fatigue. Change scores from the following outcomes will be calculated for each subject.

Descriptive statistics will be used to describe the results across patients and paired t-tests will be used to analyze the pre-post changes.

- Finger movement tracking error (squared sum distance from the target).
- Box and Block Test number of blocks successfully moved.
- Melbourne Assessment 2 percent score (0-100%).
- Assisting Hand Assessment score.

Additionally, adherence will be determined by downloading usage data from both the stimulator and the computer (via a portable USB thumb drive) – which will be used to calculate the percentage of prescribed treatment time completed by each participant. Participants will also be asked at every visit to report any difficulties or complications they may have experienced during home treatment sessions. Then, at the end of treatment, every participant will be interviewed regarding their impression of treatment and dosage, how easy or difficulty it was to use the equipment and play the games, and what changes they would suggest to the equipment or treatment dose, and whether or not they thought the treatment made any difference in their hand function. The number of hand opening repetitions will be recorded at each training session.

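### Pre-post change in finger-tracking error cannot separate practice on a similar game from better motor control; read this outcome through the between-arm difference

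*Combined protocol and SAP*

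**What the plan says.** The Outcome Measures section introduces the test with "Finger movement tracking is a method of measuring motor control". It is run "Using the same bend sensor used for controlling the video games", and the child's task is to "keep the cursor on or as close to the scrolling trace as possible by extending and flexing their index finger". The trace is a 0.1 Hz sine wave scaled to the child's own active extension, and the wrist and forearm are held still. One practice trial precedes three scored trials of 30 seconds.

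The Methods and Procedures section lists four treatment games. One of them, Sound Tracker, requires the "hand to precisely follow a moving track generated by different songs". Games are phased in: "As proficiency with one game develops, more games will be introduced". On allocation, the section says "both groups will receive the same task practice and video game training"; only the experimental arm receives stimulation. The dose is given as "10 sessions per wk of self-administered video game training at home plus 2 lab sessions per wk for the first 3 wks", then one lab session per week for the last three weeks, 58 hours in all.

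The Data analysis section lists "Finger movement tracking error (squared sum distance from the target") as one of four change-score outcomes. The only test it names is a paired t-test of pre-post change. Assessments are made without stimulation, at least 24 hours after the last treatment session.

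**The concern.** The test and one of the games share a sensor and a goal, namely following a moving target by opening and closing the hand. Children may therefore improve on the test because they have practised something like it for six weeks. The plan does not mention this overlap, does not withhold the game, does not include an untrained tracking pattern, and does not say how learning of the task will be told apart from better control.

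The choice of test makes this matter. A pre-post comparison has no control for practice, so any gain from the games counts in full. If a significant fall in tracking error were reported as evidence that the combined therapy works, or that its benefit carries over to hand function, the analysis could not support that statement.

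**Working it through.** **1. The two tasks side by side**

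| Feature | Tracking test | Sound Tracker |
|---|---|---|
| Sensor | Bend sensor used for the games | Bend sensor |
| Goal | Stay on a scrolling trace | Follow a moving track precisely |
| Target | Fixed 0.1 Hz sine | Generated by different songs |
| Movement | Index finger, wrist and forearm stabilised | Hand opening and closing |
| Stimulation | None | CCFES arm only |

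Sensor and goal agree; target, movement and (in one arm) stimulation differ. The game's display, speed and scoring are not described, so the closeness cannot be judged further.

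**2. How much practice might be involved**

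Inputs are from Methods and Procedures.

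- Home sessions: 10 × 6 = 60. Lab sessions: 2 × 3 + 1 × 3 = 9.
- The stated total of 58 h is consistent with 9 lab sessions of 1.5 h (13.5 h) and home sessions of (58 − 13.5)/60 h, or 44.5 min.
- Task practice in the lab is up to 9 × 0.75 = 6.75 h, which leaves 58 − 6.75 = 51.25 h. This counts all home time as games, although home sessions also include hand-opening exercises.
- Equal sharing among four games gives 51.25/4 = 12.8 h of Sound Tracker. Shares of 10% and 50% give 5.1 h and 25.6 h.

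The share is not in the documents, so these hours only illustrate possible exposure. They do not measure bias.

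**3. What a pure practice gain does to each comparison**

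Write a child's change as practice gain *g* plus true change *c* plus noise. A paired test examines *g* + *c*. The between-arm difference in mean change is (*c*₁ − *c*₂) + (*g*₁ − *g*₂), so a common *g* drops out.

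Set true change to zero in both arms. Assumptions: two-sided alpha 0.05; 10 children per arm (the plan says only 20 in total); gain *d* in SDs of the change score. The paired test statistic is noncentral t with n − 1 degrees of freedom and noncentrality *d*√n.

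| Assumed gain *d* | P(significant), n = 10 | P(significant), n = 20 pooled |
|---|---|---|
| 0.2 | 9% | 14% |
| 0.3 | 14% | 25% |
| 0.5 | 29% | 56% |
| 0.8 | 62% | 92% |
| 1.0 | 80% | 99% |

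For a two-sample t-test of change, 10 against 10, there are 18 degrees of freedom and the noncentrality is (difference in gain)/√(2/10):

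| Difference in gain between arms | P(significant) |
|---|---|
| 0 | 5% |
| 0.3 | 10% |
| 0.5 | 19% |

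The within-arm or pooled test responds to the whole practice gain, the between-arm test only to the part that differs by arm.

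**The case against.** The strongest reply is that the design already handles this. Both arms play the same games at the same prescribed dose, and the study question is games with stimulation against games alone. Practice common to both arms cancels in that comparison. This stands. The remaining difficulty is that the analysis section names no between-arm test, an omission that affects all four outcomes.

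Second, the test is not the game. The differences in target, movement and stimulation are real, and some of any gain may be true motor control. This also stands, so it would be wrong to say that the children simply rehearse the test.

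A reader might infer several stronger things that the documents do not support:

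- *That the CCFES arm will play Sound Tracker more and so gain an unfair advantage.* Games are added with proficiency, and a game that causes motion sickness is avoided, so exposure can vary. Nothing shows which arm would have more. The bias could also run against CCFES, because controls practise unassisted, as they are tested.
- *That the other three outcomes are untrained.* Clinic sessions include functional task practice in play and daily activities, which may overlap with those tests, though less directly.
- *That tracking will supply the effect for the larger trial, or is claimed to show transfer to function.* The sample size section names no outcome for planning, and tracking is described only as a measure of motor control.
- *That tracking is the outcome most likely to look positive.* No figure in the documents bears on this.

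**Conclusion.** The point holds in a limited form. With the only test the plan names, improvement in tracking error cannot be assigned to motor control rather than to practice on a similar task. The between-arm difference is largely protected. It is exposed only if Sound Tracker exposure, or the carry-over from assisted as opposed to unassisted practice, differs between arms, and the direction is unknown.

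The size of the practice gain cannot be found from the documents. The probabilities above rest on assumed gains, an assumed alpha and an assumed equal split, and the figure of about 13 h rests on equal sharing of games. One outcome of four in a 20-child pilot is affected. I rate it a minor-to-moderate interpretive point.

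**What to change.** In the Outcome Measures and Data analysis sections:

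1. Describe finger tracking as a measure close to a trained task.
2. State that its pre-post change will not be taken as evidence of efficacy or of transfer to function.
3. State that it will be interpreted through the between-arm difference in change from baseline, reported with a confidence interval.
4. Report Sound Tracker minutes per child by arm beside that result. The plan promises usage data but not time per game, so first confirm that the logs record it; if they do not, state this as a limitation.
5. If tracking is used to plan the larger trial, use only the between-arm estimate and carry this caveat with it.

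The cost is some wording and one descriptive table. The downside is that one of the four outcomes supports a narrower claim.

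Separately, when these sections are edited, reconcile the two definitions of tracking error: an average vertical distance in Outcome Measures and a squared sum in Data analysis. The argument here does not depend on which is used.

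### As written, the game-play repetition rule does not count hand openings: it gives two counts per open-close cycle and also counts small reversals (minor priority)

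*Combined protocol and SAP*

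**What the plan says.** The combined protocol and SAP lists the number of hand-opening repetitions under Outcome Measures, to be counted in task practice and in game play. The only counting rule is for games: "repetitions are detected by a change in the sign of the first difference (analogous to finger velocity) of the bend sensor signal". No method is given for task practice.

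The count is used in two places. Outcome Measures states: "We will use the total number of repetitions for correlations". The Data analysis section opens with a descriptive approach, using means and robust standard errors, "to assess the effect of hand opening repetitions on the treatment group over time for each outcome". That section later adds "The number of hand opening repetitions will be recorded at each training session", but no further definition.

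Three other statements bear on the signal. The Rationale says that play consists of opening and closing the paretic hand. In Methods and Procedures, Sound Tracker needs the "hand to precisely follow a moving track generated by different songs". For the clinic sessions, the same section says "As proficiency with one game develops, more games will be introduced".

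**The concern.** The quantity is named as hand openings, but the rule detects velocity reversals. These differ in two ways.

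- **Two reversals per cycle.** An open-close cycle reverses once at full opening and once at full closing. If both count, each opening scores 2.
- **No size limit.** A small correction or a flicker of sensor noise reverses the sign just as a full opening does. Counting one direction removes the doubling but not this. Corrections are plausible in a tracking game, and children may play different mixes of games as games are added.

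At stake is the exposure variable of the repetition analysis. A count that depends partly on how slowly or unsteadily a child moves is not a clean measure of dose, and the reported totals would not be numbers of openings.

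**Working it through.** The plan states no repetition count, so there is no figure of its own to reproduce. The check applies the rule as written to artificial signals.

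**1. Clean signal.** Thirty open-close cycles over 300 s gave 59 sign changes, that is, 2 per cycle with one turning point lost at the edge of the record. Counting opening-to-closing reversals only gave 30.

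**2. Sensor noise, no filter.** Same 30 cycles at 0.1 Hz between 15% and 85% of range (both borrowed from the finger-tracking test in Outcome Measures). White noise with an SD of 0.1% of range is an assumption, as is the sampling rate.

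| Sampling rate | Sign changes | Per cycle | One direction only |
|---|---|---|---|
| 20 Hz | 344 | 344/30 = 11 | 172 |
| 50 Hz | 2,231 | 2,231/30 = 74 | 1,115 |
| 100 Hz | 9,825 | 9,825/30 = 328 | 4,912 |

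Direction plus an illustrative 20% minimum excursion gave 30 in every row.

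**3. Small corrective wobble.** The signal is 50 + 35 sin(2πft) + A sin(2π·1.5t), with random phases, sampled at 50 Hz. The 1.5 Hz wobble, its amplitude A (% of range) and the low-pass filter are assumptions. Mean sign changes per opening with a 5 Hz filter, where 2.0 means nothing added:

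| Openings/min | A = 0.5% | A = 1% | A = 3% |
|---|---|---|---|
| 6 | 4.1 to 4.4 | 8.3 to 8.7 | 30 |
| 15 | 2.0 | 2.0 | about 4 |
| 30 | 2.0 | 2.0 | 2.0 |

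The ranges are means from repeated runs with different random phases.

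Analytic check: the wobble can add a reversal only if A > 35(f/1.5)². At 6/min (f = 0.1) this is 35 × 0.00444 = 0.16%; at 15/min, 0.97%; at 30/min, 3.9%. It reverses velocity on every wobble cycle if A > 35f/1.5, which is 2.3% at 6/min. There are then 1.5 × 10 = 15 wobbles per opening and 15 × 2 = 30 counts, as simulated.

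The filter is decisive. At 6/min with A = 3%, a 2 Hz filter left about 26 counts per opening and a 1 Hz filter about 4. With the 1 Hz filter, wobble up to 1% gave about 2.0 at 6, 15 and 30/min.

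**4. Mixed units.** Methods and Procedures gives 2 × 3 + 1 × 3 = 9 clinic sessions. At the full 90 min these take 9 × 1.5 = 13.5 h, half of it games (6.75 h) and half task practice (6.75 h). Of the 58 h total, 58 − 13.5 = 44.5 h is at home. Let s be the share of home time spent on games and k the ratio of the task-practice opening rate to the game rate. With games counted twice and task practice once, the total is inflated by

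(2g + 6.75k)/(g + 6.75k), where g = 6.75 + 44.5s.

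- s = 1, k = 1: g = 51.25; (102.5 + 6.75)/(51.25 + 6.75) = 109.25/58 = 1.88.
- s = 0.5, k = 4: g = 29; (58 + 27)/(29 + 27) = 85/56 = 1.52.
- s = 1, k = 0.25: (102.5 + 1.69)/(51.25 + 1.69) = 104.19/52.94 = 1.97.

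The values of s and k are assumptions. A share below 1 is possible because, of home sessions, the plan says "These consist of CCFES-mediated hand opening and video game exercises".

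**5. Effect on a correlation.** corr(2X, Y) = corr(X, Y), so uniform doubling of game counts changes nothing. Inflation that varies between children does not cancel. Its effect on the correlation cannot be computed, because the documents give no inputs for it.

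**The case against.** The strongest reply is that this is shorthand for a rule that works. The measure is named after hand openings, so counting one direction is a natural reading. The software may well smooth the signal, and a short protocol may leave sampling and filtering to device documentation. Doubling alone is harmless to a game-count correlation. The large figures come from assumed noise, wobble and filters; with a strong filter or fast movement the inflation vanishes. The analysis is descriptive, in a pilot whose 20 places were set by funding. Even with perfect counts, r = 0.5 has a 95% CI of 0.07 to 0.77 at n = 20 (Fisher z), and of −0.19 to 0.86 if the treatment group means one arm of about 10. Counter error may be a small part of that uncertainty.

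Most of this stands, and it limits the priority. A reader might take the extreme case (30 counts per opening at 6/min against 2.0 at 30/min, a 15-fold contrast) as the expected error. The documents do not support that, since they give neither the children's opening rates nor the filter. Nor do they show that the software really counts every reversal.

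The reply does not supply a definition. The sentence is complete, it describes an algorithm, and nothing elsewhere narrows it. Counting one direction, even if intended, leaves small reversals in.

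**Conclusion.** The point holds as a minor one. Read literally, the rule gives 2 counts per open-close cycle on a clean signal, or 1 if one direction is meant, and counts small reversals as repetitions. The first figure needs no assumption beyond the literal reading. The further inflation is of unknown size: none to very large under the assumptions tried. If task practice is scored once per opening, the reported total is 1.52 to 1.97 times the true number of openings over the assumed ranges, from the doubling alone.

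Unequal inflation between children can distort the repetition-outcome correlation, by an amount not quantified here. A reader might infer that the trial's efficacy results are compromised. They are not: tracking error, Box and Block, Melbourne Assessment 2 and Assisting Hand Assessment, and their paired t-tests, do not use the counter, and adherence is a percentage of prescribed time.

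**What to change.** In Outcome Measures, define one game-play repetition as one opening-to-closing reversal of the smoothed bend signal after an excursion above a prespecified fraction of the child's calibrated range. State the sampling rate, filter and fraction. Choose the fraction from recorded game signals without reference to outcomes, apply it identically in both arms and all games, and report the count at one or two other fractions as a sensitivity check. Count task practice as one per opening too, or analyse it separately. If the software already does something of this kind, writing it down is enough.

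Save the bend signal so that counts can be rerun. The plan says the self-report ratings are "saved to the USB drive along with game usage and performance data" and does not name the raw signal there; sessions already held can be recounted only if it was kept.

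The cost is a small code change, a few sentences and lower reported totals. Some true small openings will be lost, mostly in children with small movements. In simulation with variable excursions (assumed log-SD 0.6), a 20% threshold counted 0.97 to 1.00 per opening at a median excursion of 70% of range, but 0.49 to 0.72 at a median of 20%. A 10% threshold counted 0.89 to 1.00 at that smaller median. A 5% threshold overcounted slow movers with a 3% wobble (1.8 to 5.9 per opening at 6/min). These figures show why the fraction needs the sensitivity check; they do not settle its value.
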